13.1.1. Secondary Aims

- 1. Test the efficacy of PREVENT to increase perceived access to care over 12 months (secondary outcome). Hypothesis: PREVENT will increase Patient Satisfaction Questionnaire-18 (PSQ-18) scores to a greater extent than EUC over 12 months.
- 2. Test the efficacy of PREVENT to increase realized access to care over 12 months (secondary

outcome). Hypothesis: PREVENT will increase the number of received Diabetes Quality Metrics to a greater extent than EUC over 12 months.

3. Test the efficacy of PREVENT to improve DM self-care over 12 months (secondary outcome). Hypothesis: PREVENT will improve Diabetes Self-Care Inventory (DSCI) scores to a greater extent than EUC over 12 months.

Analyses: For Secondary Aims 1 – 3, we will model PSQ-18 scores, number of received Diabetes Quality Metrics, and DSCI scores as continuous variables to estimate average change in each of these three variables over time by treatment group. We will use mixed effects linear regression with fixed effects for time (baseline, and months 6 and 12), randomization assignment, and time by randomization interaction. A random intercept term and an appropriate covariance structure will be used to account for correlation among repeated measurements. Within this model we will estimate the average change in PSQ-18 scores, number of received Diabetes Quality Metrics, and DSCI scores, respectively, by treatment group, from baseline to 6 months, from 6 to 12 months, and from baseline to 12 months. For each of these 3 Secondary Aims, the primary hypothesis will be tested by comparing the groups with respect to change from baseline to 12 months.

4. Determine if increasing subjective and/or objective indicators of access to care and/or DM self-care mediates PREVENT's reduction of DM-related ED visits and/or hospitalizations. Hypothesis: PREVENT will reduce DM-related ED visits and/or hospitalizations to the extent that it increases subjective and/or objective indicators of access to care and/or improves DM self-care.

Analysis: We will use structural equation modeling (SEM) to evaluate this aim, and will simultaneously model the DM-related ED visit/hospitalization count and each proposed mediator separately (i.e., PSQ-18 scores, number of received Diabetes Quality Metrics, and DSCI scores). The model will have paths from treatment to ED visit/hospitalization count (direct effect), treatment to mediator, and mediator to ED visit/hospitalization count. Using MPlus software, we will fit the SEM model and calculate the total indirect effect for the mediator. Mediation of the treatment effect on reduced incidence of DM-related ED visits and/or hospitalizations will be considered present if there is a significant path from treatment through the mediator to the primary outcome (i.e., an indirect effect). Standard errors will be calculated using bootstrapping. If there is evidence of mediation for more than one of the proposed mediators, we will fit a model that simultaneously considers the effect of the multiple mediators.

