- 8) Undergoing medical clearance for a detox center or any involuntary court or magistrate order
- 9) Lives in assisted living, currently in a rehabilitation facility (other than Jefferson), lives in a nursing home or skilled nursing facility

[figure not shown]
10) Pregnancy

- D. Participant Enrollment: Participants will be recruited from the emergency department (ED) at Thomas Jefferson University and affiliated hospitals.
- E. Informed Consent: Informed consent will be obtained in the ED by the ED Research Coordinators or in patients' homes by a study assessor.
- F. Participant Follow-Up. Participants will be assessed at baseline, 6, and 12 months.

Table 1. Design Summary

Objective	Determine the efficacy of PREVENT to prevent ED visits and	
	hospitalizations among African Americans with diabetes	
Major Eligibility Criteria	1) African American race	
	2) Age ≥ 40 years	
	3) Diabetes	
	4) Recent ED visit	
Randomization Unit	Person stratified by HbA1c level (7.5% - 9% vs. ≥ 9%), ED	
	discharge status (i.e., home vs. hospital admission), and whether	
	or not the participant has a Jefferson PCP	
Treatments	PREVENT (n = 115)	
	EUC (n = 115)	
Recruitment Site	Emergency Department	
Enrollment Site	Emergency Department or participants' homes	
Outcome Measures	Primary: Number of diabetes-related ED visits and	
	hospitalizations over 12 months	
	Secondary: Scores on Patient Satisfaction Questionnaire;	
	number of received diabetes quality metrics; scores on Diabetes	
	Self-Care Inventory	
	Exploratory: Depression; diabetes health beliefs; all cause	
	incident ED visits/hospitalizations; glycemic control; quality of life	
Sample Size	230 (only 156 were randomized due to the pandemic)	
Masking Procedures	This is a single blind study in which the Outcome Assessor will be	
	masked but participants, interventionists, and Primary Care	
	Physicians (PCPs) will not	
Study Visit Schedule	Assessments: Baseline, 6, and 12 months	
	Interventions: 6 in-home sessions of PREVENT or EUC, followed	
	by booster sessions at months 6, 8, and 10	
Length of Follow-up	12 months	

Figure 1. Flow Chart and Study Design

3: ORGANIZATIONAL STRUCTURE

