5.7. Randomization to Treatment Group

Randomization will follow a fixed scheme with a 1:1 allocation ratio. Randomization is stratified by HbA1c level (< 9.0% vs. $\ge 9.0\%$), ED discharge status (discharged home or admitted to the hospital), and by whether or not the participant has a Jefferson PCP. The study statistician ([name]) will use a random numbers table to assign participants, and will base the schedule on a permuted random block design (with randomly chosen block sizes) to ensure balance between treatment groups on enrollment time. Randomization assignments will be loaded into a REDCap database and participants will be randomly assigned using the REDCap randomization facility. The Project Director will randomize participants once [name] confirms eligibility criteria. Treatment sessions for all participants will begin 1 to 2 weeks after randomization. Figure 2 details the work flow for participant enrollment and randomization.

Table 2. Summary of Procedures for Determining Inclusionary/Exclusionary Criteria

African American race	EMR	EMR check by ED staff
Age	EMR	EMR check by ED staff
Diabetes diagnosis	EMR	EMR check by ED staff
Rule out dementia/cognitive	Montreal Cognitive	Part 2 Baseline assessment
impairment	Assessment (MOCA)	conducted by Outcome Assessor;
		test results interpreted by PI
Rule out suicidal ideation and DSM-	EMR	EMR check by ED staff
V psychiatric disorders other than		
anxiety or nonpsychotic depression		
Rule out medical conditions that	EMR	ED attending
preclude participation		
Rule out anti-dementia medication	Self-report, EMR	EMR check by ED staff to
use		complete Part 1 of the Baseline
		Assessment; Self-report of
		medications during Part 2 of the
		Baseline Assessment by the
		assessor
Rule out pregnancy	EMR	EMR check by ED staff
Ineligible disposition (e.g.,	EMR	EMR check by ED staff
incarcerated; undergoing medical		
clearance for detoxification center		
or any involuntary court/magistrate		
order lives in assisted living or		
nursing facility)		

Figure 2. Workflow for Participant Enrollment/Randomization

6: SCHEDULE AND OVERVIEW OF DATA COLLECTION

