Subjective Access to Care: We will use the Patient Satisfaction Questionnaire-18 (PSQ-18) to measure subjective perceptions of access to care (higher scores reflect better access). We will test PREVENT's efficacy to increase PSQ-18 scores (secondary outcome), and also determine if change in PSQ-18 scores mediates PREVENT's treatment effect (PSQ-18 as a mediator). This 18-item instrument has demonstrated reliability and validity, and includes 7 subscales: 1) General Satisfaction (e.g., "I'm dissatisfied with some things about the medical care I receive."); 2) Technical Quality ("I have some doubts about the ability of the doctors who treat me."); 3) Interpersonal Manner ("My doctor treats me in a very courteous and friendly manner."); 4) Communication ("Doctors are good about explaining the reasons for medical tests."); 5) Financial Aspects ("I have to pay for more of my medical care than I can afford."); 6) Time Spent with Doctor ("Doctors usually spend plenty of time with me."); and 7) Accessibility ("It's hard to get an appointment right away."). Responses are scored (1 to 5) in a "strongly agree/strongly disagree" Likert format. We will also examine change in the individual subscales.

Objective Access to Care: We will measure participants' receipt of up to five American Diabetes Association-recommended DM Quality Metrics as an objective indicator of realized access to care. The 5 metrics will be: twice yearly HbA1c testing (outside the research protocol), annual blood pressure check, urine protein testing, foot exam, and influenza vaccination. We will review medical records to identify receipt of these 5 metrics. Scores will range from 0 to 5, with higher scores reflecting better achieved access to the health system. We will test PREVENT's efficacy to increase the number of received DM Quality Metrics (secondary outcome), and also determine if change in

number of received DM Quality Metrics mediates PREVENT's treatment effect (DM Quality Metrics as a mediator). For each indicator, we will count them as having occurred if the date of the event is within 30 days in either direction of the due date.

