13.1. Data Analyses

We will use descriptive statistics to characterize the sample, assess randomization success, and as a final data quality check. We will analyze survey metrics (e.g., treatment satisfaction with PREVENT and EUC) by summing responses across items and reporting means and SDs. For outcome analyses, we will use an intent-to-treat approach (i.e., all participants with any follow-up data are included as randomized). Any missing data are considered missing at random (MAR); we will apply models that yield valid estimates under this assumption. For analyses of continuous outcomes, we will check assumptions of normality and homoskedasticity of errors using checks of model residuals. We will transform outcomes as appropriate prior to analyses and will use SPSS, SAS, TreeAge Pro, and Mplus software as indicated.

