13.1.1. Primary Aim

Test the efficacy of PREVENT to reduce the number of incident DM-related ED visits and/or hospitalizations over 12 months (primary outcome). Hypothesis: PREVENT will halve the number of incident DM-related ED visits and/or hospitalizations relative to EUC over 12 months.

Primary Statistical Approach: The primary outcome measure is a count of DM-related ED visits and/or hospitalizations. We will use Poisson regression to model the number of outcome events as a function of randomization assignment, adjusting for the stratification variables and using follow-up time as the offset term. We will consider baseline variables (e.g., age, sex, education, cognitive functioning, insurance, polypharmacy (i.e., taking ≥ 5 medications), and medical comorbidity) as possible covariates if they relate to outcome events at the bivariate level with p<0.2. Negative binomial regression will be considered if there is evidence of over- or under-dispersion of the data.] From the model, we will calculate estimates of annual rates of the primary outcome and the adjusted estimate of the rate ratio. We will evaluate the primary hypothesis by testing the null hypothesis that the rate ratio for randomization assignment equals 1.

To examine the impact of treatment adherence on outcomes, we will calculate the Complier Average Causal Effect (CACE) and compare it to the intent-to-treat estimate. We will define adherent participants as those who: 1) receive ≥ 4 of 9 treatment sessions, and 2) have a telehealth visit with the PCP, and 3) achieve ≥ 2 DM self-care treatment goals. CACE will estimate treatment effects by comparing the outcomes in adherent PREVENT participants vs. EUC participants who would have been adherent had they been assigned to PREVENT. The adherence status for EUC participants, however, is not observable. Through the use of a latent class model, the CACE is estimable under certain assumptions. Part of the model includes using baseline covariates and adherence status in PREVENT participants to predict adherence status in EUC participants. This analysis will enable us to estimate the impact of adherence on study outcomes.

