13.1.3. Exploratory Aims

- 1. Determine whether PREVENT reduces "all cause" ED visits/hospitalizations relative to EUC. Analysis: We will use the Poisson regression approach described in the analysis of the primary aim.
- 2. Determine if Community Need Index score, literacy, age, and/or sex moderate treatment effects. Analysis: We will explore moderation effects by extending the models above to include randomization assignment by moderator interaction terms, and estimating treatment effects for different levels of the moderator. We will consider treating the moderators as continuous variables under a linear assumption, and as categorical variables categorized in clinically meaningful ways, by quartiles, or at the median. As the literature on sex differences on ED use in AAs is scant, we are unable to formulate specific hypotheses regarding the relationship of sex to study outcomes. If our data suggest differences by sex, we will conduct supplementary analyses to delineate potential

mediators of these differences. We will also examine whether "built environment" indicators (i.e., neighborhood safety, transportation difficulties, and access to healthy foods) moderate treatment response.

- 3. Determine if PREVENT improves glycemic control (i.e., lowers HbA1c levels), impacts DM-related Health Beliefs, reduces depression, and/or improves quality-of-life.

 Analyses: For these continuous outcomes we will use the mixed effects approach described above.
- 4. Identify the treatment features of PREVENT which confer its cultural relevance. Analysis: We will use descriptive statistics to characterize responses on the Cultural Relevance Rating Form in participants assigned to PREVENT. If ≥ 75% of participants rate an item ≥ 7 [from 1 to 10 (more valued], that aspect of treatment will be considered to be culturally relevant.
- 5. Evaluate PREVENT's costs and net financial benefit.

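### Secondary and exploratory continuous outcomes are compared on change from baseline without adjusting for the outcome's own baseline value; valid, but usually less precise than using that value as a covariate

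*Combined protocol and SAP*

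**What the plan says.** Section 13.1.1 (Secondary Aims, Analyses) specifies a linear mixed model for PSQ-18, the number of Diabetes Quality Metrics and the DSCI score, with "fixed effects for time (baseline, and months 6 and 12), randomization assignment, and time by randomization interaction". A random intercept and a covariance structure to be chosen later handle the repeated measures. For each aim, "the primary hypothesis will be tested by comparing the groups with respect to change from baseline to 12 months". Section 13.1.3 extends this to HbA1c, health beliefs, depression and quality of life: "For these continuous outcomes we will use the mixed effects approach described above".

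Baseline is therefore a response, and each arm has its own baseline mean. No section enters the outcome's own baseline as a covariate or sets a common baseline mean. Section 6.2 and Table 5 list other possible covariates, such as personal characteristics, literacy, MOCA and comorbidity. Section 12.1 allows control for variables that differ between completers and dropouts. Adjustment for the stratification factors appears only in the primary count model, "adjusting for the stratification variables and using follow-up time as the offset term".

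**The concern.** Subtracting baseline fixes its coefficient at 1. When the baseline to month-12 correlation is moderate, the best coefficient is smaller, and the subtraction adds baseline noise to the treatment comparison. With equal SDs and a correlation below 0.5, the change comparison is less precise than comparing month-12 values alone.

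The stake is precision, not bias. It matters more here because 156 of the planned 230 were randomized, and because the baseline scores have been collected anyway.

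HbA1c is a special case. Section 5.7 says "Randomization is stratified by HbA1c level", so the arms are partly balanced on baseline HbA1c by design. Baseline level predicts change through regression to the mean, and the planned test gives no credit for that balance. Its reported standard error is therefore too large. The documents give no basis for saying the same of the other outcomes.

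**Working it through.** The plan states no detectable difference, SD or correlation for these outcomes, so there is no figure to reproduce.

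**Inputs.** From the documents: 78 per arm (section 5.1), 1:1 allocation (section 5.7), assessments at baseline, 6 and 12 months. Assumed: two-sided 5% level, 80% power, month-12 SD = 1, correlation r from 0.3 to 0.8, and k = baseline SD / month-12 SD.

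**Is the planned test a change-score test?** One complete simulated data set was fitted with the planned model at each of r = 0.3, 0.5 and 0.7. The month-12 interaction equalled the raw difference in mean change each time (0.4736, 0.4315, 0.4628).

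**Is it biased?** No. With a true effect of 0.30 and 5,000 replicates, mean estimates at r = 0.3, 0.5 and 0.7 were 0.304, 0.297 and 0.300 (change) and 0.303, 0.296 and 0.300 (baseline covariate).

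**Precision, complete data.**
- Variance of the change contrast: (1 + k² − 2rk) × 2/n
- Variance with baseline as covariate: (1 − r²) × 2/n
- Ratio at k = 1: (1 + r)/2
- Example, r = 0.3: √(1.4 × 2/78) = 0.1895 against √(0.91 × 2/78) = 0.1528, and 1 − 0.1528/0.1895 = 19%
- Detectable difference = 2.80 × SE

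| r (k = 1) | Variance ratio | SE, change | SE, covariate | SE gain | Detectable difference (SD) | Power of the covariate form where change has 80% |
|---|---|---|---|---|---|---|
| 0.3 | 0.65 | 0.1895 | 0.1528 | 19% | 0.53 to 0.43 | 93.5% |
| 0.5 | 0.75 | 0.1601 | 0.1387 | 13% | 0.45 to 0.39 | 89.9% |
| 0.7 | 0.85 | 0.1240 | 0.1144 | 8% | 0.35 to 0.32 | 86.0% |
| 0.8 | 0.90 | 0.1013 | 0.0961 | 5% | 0.28 to 0.27 | 84.0% |

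Simulated variance ratios at r = 0.3, 0.5 and 0.7 were 0.675, 0.754 and 0.854, close to theory.

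**Smaller baseline SD (k = 0.8).** SEs are 0.1725 vs 0.1528, 0.1468 vs 0.1387, 0.1155 vs 0.1144, and 0.0961 vs 0.0961. The gains are 11.4%, 5.5%, 1.0% and 0%. At r = 0.8 = k the best coefficient is exactly 1, so nothing is gained.

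**Missing month-12 data.** Assume per arm 62 complete, 8 with baseline and month 6 only, 8 with baseline only, and the same r between all visits. If the baseline-only participants stay in the planned model, the SEs are 0.2043 vs 0.1708, 0.1741 vs 0.1546, 0.1358 vs 0.1270, and 0.1112 vs 0.1065. The gains are 16%, 11%, 6% and 4%. Section 13.1 limits the analysis set: "all participants with any follow-up data are included as randomized". Leaving the 8 out raises the planned SE at r = 0.3 to 0.2078, a gain of 1 − 0.1708/0.2078 = 18%. Over the four correlations the gains become about 18%, 12%, 7% and 5%.

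**HbA1c under the null.** Simulation: 156 participants, 8 strata, permuted blocks of 2, 4 and 6, HbA1c cut at an assumed 50th or 70th percentile, the other two factors unrelated to outcome, equal correlation between visits, 6,000 replicates.

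| r | Planned test rejects (50th / 70th percentile cut) | Baseline-covariate form rejects |
|---|---|---|
| 0.3 | 3.0% / 2.6% | 5.4% / 4.7% |
| 0.5 | 3.2% / 3.7% | 4.5% / 5.5% |
| 0.7 | 4.1% / 3.7% | 5.4% / 4.7% |

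At r = 0.3 the planned model reports an SE of 0.189, while the estimate actually varies with SD 0.171 or 0.169. A separate simulation gave about 2.5% to 4.6% for the planned test. Adding the HbA1c stratum to the covariate form left rejection at 4.7% to 5.6% and gave no further SE gain.

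**The case against.** The strongest reply is that this is a preference. A mixed model with a time-by-arm contrast is coherent, is unbiased, and matches hypotheses worded as a greater increase than control. No stated power figure fails, because none is given for these outcomes. That stands, and it is why the point concerns efficiency only.

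The gain is not fixed by the documents. The largest figure needs r = 0.3 and equal SDs, and plausible inputs take it to zero. That also stands. However, under the large-sample formula the covariate form is never less precise, since (1 + k² − 2rk) − (1 − r²) = (k − r)², which cannot be negative.

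The HbA1c result depends on block sizes and a stratum split that the documents do not give, and it shows a conservative test, not an inflated error rate. HbA1c is also labelled inconsistently: section 6.2 calls it secondary, Table 5 and section 13.1.3 exploratory. These points limit its weight but do not reverse it.

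Lastly, recruitment has ended and several study leaders are unmasked (section 8.2). The documents do not show whether outcomes have been seen by arm. If they have, the revised model could only be a labelled sensitivity analysis.

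**Conclusion.** The concern holds as an efficiency point. The planned test is valid, but it does not use the outcome's own baseline as a covariate. With 78 per arm, equal SDs and complete data, doing so would cut the standard error by 5% to 19% for correlations from 0.8 down to 0.3. The gain is smaller, and can vanish, if baseline SDs are below month-12 SDs. For HbA1c the planned test is also mildly conservative under the simulated stratified randomization. All sizes rest on assumed correlations, SDs, missingness and block sizes. The primary analysis is not affected. The change should be made, because its cost is small, but the present plan is not in error.

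**What to change.** In section 13, for Secondary Aims 1 to 3 and the continuous exploratory outcomes, model months 6 and 12 as the responses, with the outcome's baseline value as a covariate interacting with time. Keep the month-12 treatment contrast as the test. The planned model can stay for describing change within each arm.

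- A model with a common baseline mean is an alternative only where baseline was measured before randomization.
- Stratification factors may be added for consistency with the primary model, with little expected gain in precision.
- For HbA1c, use the baseline-covariate form. Do not add the HbA1c stratum as a main effect to a common-baseline model, because the stratum is defined from a value that is itself a response there.

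Two points need settling first. Table 1 gives the strata as "Person stratified by HbA1c level (7.5% - 9% vs. ≥ 9"%), while section 5.7 splits below 9.0% against 9.0% and above; these must be reconciled. Baseline Quality Metrics must be confirmed to count only care before randomization: section 6.7 places chart review after randomization, and section 6.2 says "we will count them as having occurred if the date of the event is within 30 days in either direction of the due date".

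The cost is a short addition to the text, using the same data and software. The model takes slightly more specification, and a participant missing a given baseline score drops out of that analysis. Otherwise the analysis set of section 13.1 is unchanged. The change must be documented before outcomes are examined by arm.

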6.4. Follow up assessments

Follow-up assessments will be conducted by the assessor at months 6 and 12 in participants' homes. Biweekly, the Study Coordinator will generate a computerized list of participants who are due for their follow-up assessments within the upcoming 2-week period. Included on the list will be the date of the last assessment for each participant as well as the ideal date that the assessment should take place. The date of randomization will determine when the follow-up assessments should occur. For example, if the randomization date was 3/1/17, ideally the 6-month assessment should take place on 9/1/17. Follow-up assessments will be timed so as to take place within 7 days of the ideal assessment date. If unforeseeable events prevent the follow-up assessment from occurring on time, an Out of Window Form will be completed. We will not attempt to conduct follow-up assessments on participants who are more than 30 days past due for their follow-up assessment. If a participant misses their 6 month assessment, we will attempt to contact them when they are due for their 12 month assessment.

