6.6. Missed Assessments

If a 6 or 12 month assessment is not conducted within the allowable time window, which is 30 days on either side of the target date for the follow-up assessments, it will be designated as a missed visit. The Project Director and PI reserve the right to make exceptions to this policy (e.g., illness). If any part of an assessment is conducted within the allowable time window but the entire assessment is not completed, it will be designated as an incomplete assessment.

If a participant misses a scheduled assessment, the Outcome Assessor will contact the participant to reschedule the assessment prior to the end of the visit window. If the participant is unable to complete an assessment within the acceptable visit window, the Outcome Assessor will complete a "Missed Visit Form". All attempts and contacts will be documented.

The assessor should collect what information they can by telephone. If the assessment is conducted over the telephone, any adverse experiences, hospitalizations, or other information available are recorded on the appropriate assessment forms.

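### For PSQ-18 and DSCI, Aim 4 relates the full 12-month event count to a score measured only at month 6 or 12, so many counted events precede the score that is meant to explain them

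*Combined protocol and SAP*

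**What the plan says.** **Model and decision rule.** Section 13.1.1 (Secondary Aims), Aim 4, uses structural equation modeling. The plan "will simultaneously model the DM-related ED visit/hospitalization count and each proposed mediator separately", with paths from treatment to count, treatment to mediator, and mediator to count. The rule is: "Mediation of the treatment effect on reduced incidence of DM-related ED visits and/or hospitalizations will be considered present if there is a significant path" running from treatment through the mediator to the primary outcome. The hypothesis is that PREVENT reduces events "to the extent that it increases subjective and/or objective indicators of access to care and/or improves DM self-care".

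**Outcome.** Section 13.1.1 (Primary Aim) states: "The primary outcome measure is a count of DM-related ED visits and/or hospitalizations". The aim sets the period at 12 months. Aim 4 names no shorter period.

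**Mediator timing.** Section 2 (item F) and Table 5 place PSQ-18 and DSCI at baseline and at the 6- and 12-month follow-ups. Section 6.6 allows "30 days on either side of the target date for the follow-up assessments". The Aim 4 analysis speaks of scores. Section 6.2 says the trial will "also determine if change in PSQ-18 scores mediates" the treatment effect, and says the same for the self-care score, but gives no interval. Aims 1–3 are tested on change from baseline to month 12; the plan does not carry that contrast over to Aim 4.

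**What is absent.** No section lags the mediator, limits the count to events after the score, or adjusts for events before it.

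**The concern.** A mediator has to come before the outcome it explains. In this model the arrow from score to count is drawn by assumption, while many of the counted events happened before the score was taken. Part of the fitted association may therefore run from events to scores.

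The effect depends on a sign that nobody knows. If an event lowers satisfaction or self-care scores, the path can look like mediation when there is none. If an event raises them, the path can hide real mediation or take the wrong sign.

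Aim 4 is the trial's claim about mechanism, with its own hypothesis and decision rule. The missing time point also leaves at least four analyses open (score or change, month 6 or month 12), and the choice could be made after the results are seen.

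**Working it through.** The plan gives no figure on this point, so there is none to reproduce.

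**Step 1. Share of counted events that precede the score**

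Inputs: a 12-month count from randomization; scores at months 6 and 12; a window of ±30 days (Section 6.6). Event timing is not given, so the rate pattern is assumed.

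Share before time t = cumulative rate to t ÷ cumulative rate to month 12.

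Constant rate:
- Month-6 score: (182.6 ± 30)/365.25 = 0.418 to 0.582, with 0.50 at the target date.
- Month-12 score: (365.25 − 30)/365.25 = 0.918 at the earliest allowed visit, and 1.00 at month 12.

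Other assumed patterns:

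| Rate pattern | At month 6 | Month 6 ± 30 days | Month 12 − 30 days |
|---|---|---|---|
| Constant | 6/12 = 0.500 | 0.418–0.582 | 0.918 |
| Double in month 0–1 | 7/13 = 0.538 | 0.463–0.614 | 0.924 |
| Triple in month 0–1 | 8/14 = 0.571 | 0.501–0.642 | 0.930 |
| Double in months 0–3 | 9/15 = 0.600 | 0.534–0.666 | 0.934 |
| Triple in months 0–3 | 12/18 = 0.667 | 0.612–0.721 | 0.945 |
| Half in months 0–3 | 4.5/10.5 = 0.429 | 0.335–0.522 | 0.906 |

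The month-6 share depends on the rate pattern. The month-12 share hardly does. If events between consent and randomization were also counted, the shares would be higher; Section 6.2 records those events and Aim 4 does not say whether they are excluded.

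**Step 2. What this could do to the mediator-to-count path**

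This illustrates direction; it is not an estimate. It uses 78 per arm (Section 5.1) and a rate ratio of 0.5 (Primary Aim hypothesis). Everything else is assumed: gamma frailty with dispersion 1, retest correlation 0.5, a Poisson outcome model, and no true effect of the score on events. The EUC rates tried are 0.51 and 1.0 per year. The Introduction's figure of about 40% with any ED visit per year is not from this sample. It converts to −ln(0.6) = 0.51 without overdispersion, or 1/0.6 − 1 = 0.67 under the frailty used, so it is only a loose anchor.

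Fitted rate ratio per SD of the score (true value 1.00):

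| Assumed effect of each event on the score | 6-month change, full count | 12-month change, full count |
|---|---|---|
| Loss 0.1 SD, rate 0.51 | 0.93 | 0.87 |
| Loss 0.2 SD, rate 1.0 | 0.84 | 0.71 |
| Gain 0.2 SD, range over cells run | 1.14–1.20 | 1.31–1.40 |

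A time-ordered model (6-month score, later events, adjusted for earlier events) gives 0.99–1.01.

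**Step 3. Declarations of mediation when there is none**

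Bootstrap standard error, |z| > 1.96, either sign, 1,000 trials per cell. Order: 6-month change / 12-month change / time-ordered.

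- No effect of events on scores: 0.0–0.6% in every version. The test is conservative, so this is the reference and not 5%.
- Loss 0.2 SD, rate 1.0, no direct effect of PREVENT on the score: 0.1 / 3.2 / 0.0%.
- Loss 0.2 SD, rate 0.51, direct effect 0.3 SD: 3.0 / 11.2 / 0.8%.
- Loss 0.2 SD, rate 1.0, direct effect 0.3 SD: 5.7 / 28.9 / 0.8%.
- Gain 0.2 SD in PREVENT only, rate 1.0, direct effect 0.3 SD: 0.5 / 3.2 / 0.8%, of which 0 / 0 / 0.2% are in the hypothesized direction.

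**Step 4. Quality Metrics**

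Section 6.2 scores up to five metrics from dated chart entries. HbA1c testing is twice yearly and the other four read as annual, each with a ±30-day due-date rule. The score accumulates over the same year as the events, so single metrics may precede some events. The issue there is overlap.

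**The case against.** **The score may record an earlier state.** Six of the nine sessions fall in the first four months (Section 9.1), so a month-6 score may reflect a change reached before many of the counted events. Events then precede the measurement but not necessarily the mediator. This stands as a reason to keep the full-count model. It does not show that events leave the score unchanged, and the plan states no such assumption.

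**A reader might infer that Aim 4 is likely to declare false mediation in PREVENT's favor.** The documents do not support that. Nothing in them says an event lowers PSQ-18 or DSCI. The one documented route is the Action Plan that PREVENT staff develop after an event (Section 9.1, Sessions 4–6). It would more plausibly raise DSCI and so mask mediation, although its effect on the score is not documented either. High false-declaration rates in Step 3 need a 12-month mediator, a 0.2 SD loss per event and a 0.3 SD effect of PREVENT on the score, all at once. Aim 4 does not specify the first, and the other two are assumed.

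**The remedy has its own weaknesses.** Aim 4 asks about the 12-month reduction, and a time-ordered model drops events from the most intensive treatment period. Its power is low. The months 0–6 count that it adjusts for may itself be changed by treatment. All of this stands, and it is why the time-ordered model should be added and not substituted.

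**Conclusion.** The concern holds for PSQ-18 and DSCI. It is a flaw in the stated model and not only a missing detail: whichever time point is filled in, many counted events precede the measured score.

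The 42–58% share for a month-6 score rests on a roughly constant event rate. Under the other patterns tried, the share at month 6 is 43–67%, or 34–72% with the visit window. The share for a month-12 score is at least about 91% throughout. The size and sign of any bias in the path cannot be estimated from the documents, which give no event rate for this sample, no event timing and no score change per event.

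Two wider readings should be avoided. The reverse-order argument does not carry over to the Quality Metrics, where the issue is overlap with the count. Nor does it touch the primary analysis or Secondary Aims 1–3, none of which uses a mediator-to-count path. The change should be made before Aim 4 is analyzed, as a matter of what can be claimed about mechanism.

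**What to change.** Before Aim 4 is analyzed:

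1. State the mediator's time point and, where change is used, its interval.
2. For PSQ-18 and DSCI, add a time-ordered analysis:
   - mediator: the 6-month score, adjusted for its baseline value;
   - outcome: events from the 6-month assessment to month 12, with time at risk in that window as offset;
   - adjustment for the months 0–6 event count.

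   Section 6.4 says "If a participant misses their 6 month assessment, we will attempt to contact them when they are due for their 12 month assessment", so some participants will lack the 6-month score. For them the window could start at the scheduled 6-month date, with the score handled under the rule in Section 13.1: "Any missing data are considered missing at random (MAR); we will apply models that yield valid estimates under this assumption".
3. Keep the full-count model, but report it, and any Quality Metrics mediation, as associational and not as evidence of mechanism.

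**Cost.** No new data are needed for PSQ-18 and DSCI: event dates (Section 6.2) and 6-month scores are already collected. The downsides to state are these:

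- **Power is low.** Suppose the 6-month score itself drives later events (assumed log rate ratio −0.5 per SD, rate 1.0). Simulated power is then 24% with a 0.3 SD effect of PREVENT on the score and 55% with 0.5 SD. It is 37% at 0.5 SD if 20% (31 of 156, assumed) lack month 6. If an early score change acts all year, power is 0.5–3%, against 1–5% for the full-count versions.
- **The estimand narrows** to second-half events, given earlier ones.
- **The months 0–6 count follows randomization** and may be affected by treatment, so natural indirect effects need further assumptions. Shared causes of scores and events also remain.
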